## STATISTICAL ANALYSIS PLAN

### *Sample Size calculation*

The literature reports various experiences on the use of SWE in the study of the intestine, especially in patients with chronic inflammatory bowel diseases. But no data are reported on the use of the method in patients with graft versus host disease. Hence, we consider this as a pilot study. As such, no formal sample size calculation is needed. However, based on common rules on pilot studies [10], the minimum sample size required would be of 20 subjects. In our department, given the median annual number of allogenic stem cell transplant, we plan to enroll 75 patients. As for the secondary endpoints, an equal number of age-matched patients undergone to autologous transplant will be enrolled.

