### *Study duration*

The enrollment will be start after ethic committee acceptance and will enroll during a period of 12 months. Patients will be enrolled consecutively. Data will be collected prospectively during the study course and until all patients will reached 100 days after HSCT. Data will be analyzed subsequently throughout a period of six months.

Fondazione Policlinico Universitario Agostino Gemelli IRCCS  
Università Cattolica del Sacro Cuore

Dipartimento diagnostica per immagini, radioterapia oncologica ed ematologia  
Area Ematologica

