## *Population*

Study population will include all patients submitted to allogenic stem cell transplantation who developed diarrhea > 500 ml per day suggestive for aGvHD until 100 days from transplant date. Patients submitted to autologous stem cell transplant who developed diarrhea between transplant date and engraftment achievement will constitute control population as for other infectious complications assessment.

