### *Variables and Procedures*

Within 24-48 hours from symptoms, onset full panel of stool cultures will be performed together with Clostridium toxin assessment. Multiparametric ultrasound study will be performed at the onset of the symptoms and then weekly to monitoring intestinal changes accordingly to symptoms evolution during treatment. In the case with high suspicion for aGvHD (stool culture negative, persistent or progressive diarrhea, ultrasound imaging closely suggestive for aGvHD), as per common clinical practice, colonoscopy will be required to evaluate internal macroscopy features of the bowel and to obtain histological samples for conclusive diagnosis. In the meantime steroid therapy will be started, as per common clinical practice. The only modification of this protocol to common clinical practice is represented by the addition of a non-invasive bed-side method of evaluation of the patients with diarrhea. None of the routinely performed diagnostic and therapeutic process will be modified.

All patients submitted to autologous stem cell transplant who developed diarrhea between transplant date and engraftment achievement will constitute control population. Also in this case full panel of stool culture and clostridium toxin assessment will be performed at the onset of the symptoms. Multiparametric ultrasound study will be made at symptoms onset and then weekly until symptom resolution.

Multiparametric ultrasound study will be performed by expert qualified staff as following:

The examinations will be performed at patient's bed, in supine position, with a MyLab™9 Platform (Esaote, Italy) system. Fasting is required.

US for bowel requires both low-frequency convex probes (3.3-5 MHz) and high-frequency (5–17 MHz) linear assay probes to increase the spatial resolution of the intestinal wall and to assess the wall diameter and wall layer.

The following ultrasound parameters will be collected:

- Intestinal wall thickening (normal values < 3 mm; a mean of two measurements for section will be taken, in longitudinal and transverse sections).
- Intestinal wall stratification;
- Intestinal wall flow at colorDoppler;
- Strictures;
- Free fluid (FF) within the peritoneal cavity;
- Enlarged mesenteric lymph nodes;
- Mesenteric hypertrophy.

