### *Statistical Analysis*

All variables included in the study will be first analyzed by descriptive statistic techniques. In depth, qualitative variables will be described as absolute and relative percentage frequencies. The Shapiro Wilk's test will be used to assess the distribution of quantitative variables. Data will be then expressed either as mean and standard deviation (SD), whether normally distributed, or as median and interquartile range (IQR), otherwise.

Between groups differences (allogenic vs. autologous transplant) will be assessed by the Fisher exact test and the Chi-square test, with Yates correction, as appropriate, in the case of qualitative variables. Quantitative data, indeed, will be assessed either by the Student's t test or the non-parametric Mann Whitney U test, as appropriate.

Receiver Operating Curve (ROC) analysis will be used to assess the accuracy of multiparametric bedside ultrasound in aGvHD diagnosis as compared to the histologic diagnosis (gold-standard, used as reference). Positive (PPV) and Negative predictive values (NPV), sensitivity and specificity will be computed, as well as the area under the ROC curve (AUROC).

To assess potential associations between bed-side multiparametric ultrasound measurements and aGvHD diagnosis in patients underwent to allogenic transplant uni- and multivariable logistic regression models will be used.

Logistic regression models will be also applied to assess whether bed-side multiparametric ultrasound (US) measurements differ in distinguishing complications different from aGvHD (i.e., infectious, drug-related or neutropenic colitis) in patients underwent to allogenic transplant as compared to auto-transplant. More in depth, to evaluate the combined effects between US measurements and transplant group, multivariable interaction models will be fitted, and the interaction odd ratios (IOR) evaluated. In particular, for each US measurement, one interaction logistic regression model will be fitted. In summary, the coefficients of the main effects (in exponential terms) will be interpreted as ORs of the outcome by considering the allo-transplant group from control ( $OR_{\text{autologous}}$ ), by

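### The autologous controls are defined in two ways, and the between-group analyses neither use the planned age matching nor name age as a term

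*Combined protocol and SAP*

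**What the plan says.** The controls are described in three places.

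- **Population:** "Patients submitted to autologous stem cell transplant who developed diarrhea between transplant date and engraftment achievement will constitute control population". No number and no matching is mentioned.
- **Variables and Procedures:** "All patients submitted to autologous stem cell transplant who developed diarrhea between transplant date and engraftment achievement will constitute control population". Each of these patients has ultrasound at symptom onset and weekly afterwards.
- **Sample Size calculation:** for the allogeneic group, "we plan to enroll 75 patients"; for the secondary endpoints, "an equal number of age-matched patients undergone to autologous transplant will be enrolled". There is no caliper, no statement of individual or frequency matching, and no rule for drawing the matched set.

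Study duration adds the general sentence "Patients will be enrolled consecutively", which is not specific to the autologous group.

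Under Statistical Analysis, qualitative variables "will be assessed by the Fisher exact test and the Chi-square test, with Yates correction", and quantitative variables "will be assessed either by the Student's t test or the non-parametric Mann Whitney U test". No paired or stratified version is named. The second secondary endpoint is analysed with one logistic model per ultrasound measurement. The terms described are transplant group, the measurement and their interaction. Data Collection lists age among the recorded variables, but no analysis names it.

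**The concern.** A rule that takes all eligible controls and a rule that takes an equal, age-matched number are different sampling rules, and the plan does not say how one leads to the other. Controls are imaged as they arise. If the set is later cut to a matched 1:1 group without a written rule, the choice of controls is still open after ultrasound results exist.

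The analysis does not fit either rule. With matched controls, it ignores the matching factor. With all eligible controls, nothing named in the analysis deals with an age difference between groups, although the plan treats age as important enough to match on. The comparison concerned is the second secondary endpoint: how ultrasound measurements behave for complications other than aGvHD in allogeneic as against autologous patients.

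**Working it through.** **Figure in the plan.** There is nothing to reproduce. The 75 comes from annual transplant volume, and the control number is set equal to it (75 + 75 = 150). No power, effect size or SD is given.

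**Inputs.** From the documents: 75 per group and a 0.05 significance level (taken as two-sided). Assumed, because the documents give no values: the age gap between groups, the correlation r between age and a measurement, the share of variance explained by age, and the effect of age on the outcome.

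**Case A: controls not matched, age not adjusted for; raw comparison of means.**

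In SD units, bias b = age gap × r, and SE = √(2/75) = 0.163. Type I error = 1 − Φ(1.96 − b/SE) + Φ(−1.96 − b/SE).

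| Age gap (SD) | r | b | b/SE | Type I error |
|---|---|---|---|---|
| 0.25 | 0.2 | 0.05 | 0.31 | 0.061 |
| 0.5 | 0.1 | 0.05 | 0.31 | 0.061 |
| 0.5 | 0.2 | 0.10 | 0.61 | 0.094 |
| 0.5 | 0.3 | 0.15 | 0.92 | 0.151 |
| 0.5 | 0.4 | 0.20 | 1.22 | 0.232 |
| 1.0 | 0.2 | 0.20 | 1.22 | 0.232 |
| 1.0 | 0.4 | 0.40 | 2.45 | 0.688 |

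**Case B: controls matched on age, analysed unpaired.**

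With exact age matching, the within-pair correlation ρ equals the share of variance that age explains (ρ = r²). The ratio of unpaired to true SE is 1/√(1 − ρ), and the actual type I error is 2 × [1 − Φ(1.96/√(1 − ρ))].

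| ρ | SE ratio | Actual type I error |
|---|---|---|
| 0.05 | 1.026 | 0.044 |
| 0.09 | 1.048 | 0.040 |
| 0.20 | 1.118 | 0.028 |

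A simulation of 20,000 runs with r = 0.3 (ρ = 0.09) gave 0.040 unpaired and 0.048 paired. At that ρ, power for a 0.46 SD difference is 0.815 unpaired and 0.840 paired.

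**The planned logistic model without age.** This was simulated with 75 per group and no true group effect or interaction. Age acted additively on the logit scale, and there were 4,000 runs per scenario. The scenarios crossed an age gap of 0.5 or 1 SD, r of 0.2 or 0.4, and an assumed log odds ratio for age of 0.3 or 0.7 per SD.

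- Interaction odds ratio: type I error about 4 to 5% in all eight scenarios.
- Group main-effect odds ratio: type I error from about 6% to about 40%.

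**The case against.** Five points can fairly be made for the plan.

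1. **The rules may be compatible.** The procedures text could describe the source population and the sample size text the sample drawn from it. The Population section does not say all, and the sentence on consecutive enrollment is general, while the inclusion criteria describe only allogeneic patients. This reading is possible, but the step from source to sample is still unwritten.
2. **The models are called multivariable.** Age might therefore be intended. No covariate list is given, and the coefficients that the plan interprets are group, measurement and interaction only. The accurate statement is that age is not named, rather than that it is excluded.
3. **The endpoint is answered by the interaction odds ratio.** A reader might take the Case A figures as the error rate of the secondary endpoint. They are not: they apply to the raw two-group comparison. The simulation shows that the interaction odds ratio keeps its level unless age acts differently by group or by measurement. This objection stands.
4. **Ignoring the matching is conservative.** A reader might infer that wrong standard errors produce false positives. They are too large here, so they do not. Matching is on transplant group and not on outcome, so conditional logistic regression is not required either. This also stands.
5. **Matching is a legitimate design.** A reader might infer that 1:1 matching wastes eligible controls. The documents give no autologous transplant volume or diarrhea rate, so that cannot be shown. Keeping or dropping the matching is a design choice.

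**Conclusion.** The point holds in limited form. The control definitions need reconciling, and that conclusion needs no assumption. The between-group analyses neither use the matching nor name age.

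The size of the consequence depends on which rule is followed and on assumed age effects. Without matching, the t or Mann-Whitney comparisons and the group main-effect odds ratio may be confounded. The 9 to 23% for a raw mean comparison assumes a 0.5 SD age gap and r = 0.2 to 0.4; if either the gap or the correlation is near zero, the problem disappears. With matching, the loss is standard errors 3 to 12% too large, if age explains 5 to 20% of variance.

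The documents do not support a conclusion that the results are wrong under either rule, because both cases need age to be related to the measurement or the outcome. The primary accuracy endpoint is evaluated within allogeneic patients and is untouched. Pilot status explains the absence of a power calculation, but it does not settle who the controls are.

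**What to change.** 1. Choose one control definition and use it in Population, Variables and Procedures, and Sample Size calculation. If matching is kept, state whether it is individual or by frequency, the age tolerance, the ratio, and how controls are drawn, without reference to ultrasound results.
2. Add age as a covariate in every allogeneic-versus-autologous logistic model.
3. For the between-group comparison of ultrasound measurements, report an age-adjusted regression alongside or in place of the unadjusted test.

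Items 2 and 3 help under either control definition. The cost is SAP wording and one extra parameter per model. Age is already recorded, so no new data are needed. If all eligible controls are taken, the groups may be unequal in size.

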### *Statistical Analysis*

All variables included in the study will be first analyzed by descriptive statistic techniques. In depth, qualitative variables will be described as absolute and relative percentage frequencies. The Shapiro Wilk's test will be used to assess the distribution of quantitative variables. Data will be then expressed either as mean and standard deviation (SD), whether normally distributed, or as median and interquartile range (IQR), otherwise.

Between groups differences (allogenic vs. autologous transplant) will be assessed by the Fisher exact test and the Chi-square test, with Yates correction, as appropriate, in the case of qualitative variables. Quantitative data, indeed, will be assessed either by the Student's t test or the non-parametric Mann Whitney U test, as appropriate.

Receiver Operating Curve (ROC) analysis will be used to assess the accuracy of multiparametric bedside ultrasound in aGvHD diagnosis as compared to the histologic diagnosis (gold-standard, used as reference). Positive (PPV) and Negative predictive values (NPV), sensitivity and specificity will be computed, as well as the area under the ROC curve (AUROC).

To assess potential associations between bed-side multiparametric ultrasound measurements and aGvHD diagnosis in patients underwent to allogenic transplant uni- and multivariable logistic regression models will be used.

Logistic regression models will be also applied to assess whether bed-side multiparametric ultrasound (US) measurements differ in distinguishing complications different from aGvHD (i.e., infectious, drug-related or neutropenic colitis) in patients underwent to allogenic transplant as compared to auto-transplant. More in depth, to evaluate the combined effects between US measurements and transplant group, multivariable interaction models will be fitted, and the interaction odd ratios (IOR) evaluated. In particular, for each US measurement, one interaction logistic regression model will be fitted. In summary, the coefficients of the main effects (in exponential terms) will be interpreted as ORs of the outcome by considering the allo-transplant group from control ( $OR_{\text{autologous}}$ ), by

fixing US measurements values to 0 (null), and ORs of the outcome by considering a unit increase of the US measurements in the auto-transplant group ( $OR_{US\_measurements}$ ). The interaction parameters (IOR) will be interpreted as difference (in OR terms) of the US measurements variations between transplant groups (autologous transplant as reference category).

Statistical significance will be set at P value  $< 0.05$ . P values between 0.05 and 0.10 will be further reported as suggestive. All analyses will be performed by using R software (v. 4.1.2, R Core Team, 2021) [11].

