The contrast agent is administered intravenously and excreted through the lungs without risk of nephrotoxicity or ionizing radiation as in the case of computed tomography contrast agent; it does not remain in the body longer than 15 min. It consists of microscopic bubbles of gas (size 3–5  $\mu\text{m}$ ), which are encapsulated in a shell of flexible and stiff phospholipids: they enhance the backscatter signal from blood cells, oscillating when exposed to a low-intensity US field, thereby demonstrating tissue perfusion in real-time “blood-pool”

imaging. SonoVue (SV, Bracco, Italy) is actually the second-generation US contrast agent used for CEUS, consisting of phospholipid-stabilized microbubbles filled with sulphur hexafluoride. The recommended dose of SonoVue is 2.4 mL. Every injection should be followed by a flush with 5-10 mL of 9 mg/mL (0.9%) sodium chloride solution. Approximately, 10–15 s after intravenous injection, the SonoVue arrives to the intestinal wall, thereby achieving the maximum concentration (peak intensity) after approximately 30 s. This stage is followed by a venous phase, and it is finally excreted by the lungs. No adverse event was reported with SonoVue use: the only contraindication is severe cardiomyopathy (7-9).

The following CEUS parameters will be collected:

- Time-intensity curve (TIC) included basic intensity (B), wash-out slope and/or decent slope (K), wash-in slope or rise slope (C), time to peak (TTP), area under the gamma curve (Area), arrive time (ATM), peak intensity (PI), change of peak intensity (I).
- Any exam will be recorded;
- Acquisition time: 5'

Moreover, each single evaluation will be completed with the use of SWE in order to further evaluate the characteristics of the inflammatory bowel.

SWE of the bowel wall will be performed according to manufacturer guidelines

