## ENDPOINTS

### *Primary endpoint*

Primary endpoint of the study is to evaluate the accuracy of bed-side multiparametric ultrasound study in the diagnosis of gastrointestinal aGvHD in patients underwent to allogenic transplant in terms of sensitivity, specificity, positive predictive value (PPV) and negative predictive value (NPV).

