### *Secondary endpoints*

- To assess potential associations between bed-side multiparametric ultrasound measurements weekly performed and aGvHD diagnosis in patients underwent to allogenic transplant.
- To assess whether bed-side multiparametric ultrasound measurements at baseline differ in distinguishing complications different from aGvHD (i.e., infectious, drug-related or neutropenic colitis) in patients underwent to allogenic transplant as compared to auto-transplant.

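### The primary accuracy endpoint names no index scan, index variable or positivity rule and plans no intervals or internal validation, so ROC cut-offs read from the same 75 or fewer patients would flatter it

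*Combined protocol and SAP*

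**What the plan says.** The Primary endpoint section defines accuracy "in terms of sensitivity, specificity, positive predictive value (PPV) and negative predictive value (NPV"). The Sample Size calculation calls the study a pilot, and for the allogeneic group states "we plan to enroll 75 patients".

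Variables and Procedures lists what each examination yields: seven B-mode and Doppler items, eight contrast parameters ("Time-intensity curve (TIC) included basic intensity (B), wash-out slope and/or decent slope (K), wash-in slope or rise slope (C"), time to peak, area, arrival time, peak intensity and its change), and shear wave elastography (SWE). Scans take place at symptom onset and then weekly. The weekly scans are there "to monitoring intestinal changes accordingly to symptoms evolution during treatment", and a secondary endpoint concerns "bed-side multiparametric ultrasound measurements weekly performed and aGvHD diagnosis".

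The analysis is in one short paragraph of Statistical Analysis: "Receiver Operating Curve (ROC) analysis will be used to assess the accuracy of multiparametric bedside ultrasound in aGvHD diagnosis", with histology as reference, followed by the four accuracy measures and the AUROC. Logistic models are planned separately, for association. Data Collection records ultrasound findings but no overall positive or negative result.

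**The concern.** Sensitivity and specificity belong to a binary result. A multiparametric scan with sixteen listed parameters becomes binary only once someone states which scan counts, which parameter or combination is the test, and where positive begins. The plan states none of these.

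If the threshold is then read from the ROC curve of the same patients whose accuracy is reported, it is tuned to chance features of that sample. The resulting sensitivity and specificity, and the PPV and NPV from the same 2x2 table, are better than new patients would show. This happens even when the marker was chosen in advance. Picking the best of several markers adds to it. With no intervals planned, readers would also not see how imprecise the figures are.

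**Working it through.** **Is the test defined anywhere?**
- Index scan: onset is the natural reading, because the weekly scans have a monitoring role and their own secondary endpoint. The Primary endpoint section does not say so.
- Index variable: 7 B-mode/Doppler items + 8 time-intensity parameters + 1 SWE = 16 candidates, none singled out.
- Positivity rule: two items come close. Wall thickness has a normal limit of 3 mm, but that is a normal range for one parameter and not a rule for a positive multiparametric scan. The phrase "ultrasound imaging closely suggestive for aGvHD" implies an overall reading, but it is undefined.
- Intervals, bootstrap, cross-validation or a validation sample: none in the sample size or analysis sections.

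**Is there a figure to reproduce?** No. The 75 comes from annual transplant volume, and no precision target is given.

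**How many patients?** 75 is a ceiling, because histology follows only in high-suspicion cases. The Introduction gives aGvHD in 40-80% of recipients with intestinal involvement in 60% of those, so 0.40 × 0.60 = 24% to 0.80 × 0.60 = 48% of recipients. Patients with diarrhoea will have a higher share, which the documents do not give. I assumed 24% to 75%, or 18 to 56 cases out of 75.

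**How large could the overstatement be?** Assumptions: all 75 have histology; one marker chosen in advance, normal with equal variance in cases and non-cases; the cut-off c maximises sensitivity + specificity (Youden) in the same 75. Marker shift d = √2 × Φ⁻¹(AUROC). At that cut-off, new-patient sensitivity = 1 − Φ(c − d) and specificity = Φ(c). The overstatement is apparent minus new-patient (sensitivity + specificity), averaged over 3000 simulated studies per cell, in percentage points. The last column is half the sum.

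| True AUROC | 18 cases | 27 | 36 | 45 | 56 | Average per measure |
|---|---|---|---|---|---|---|
| 0.76 | 12.0 | 10.4 | 9.9 | 10.0 | 12.1 | 5-6 |
| 0.86 | 10.5 | 9.0 | 8.6 | 8.8 | 10.2 | 4-5 |
| 0.92 | 9.2 | 8.1 | 7.4 | 7.6 | 9.4 | 4-5 |
| 0.985 | 6.7 | 5.6 | 5.0 | 5.2 | 5.9 | about 3 |

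Repeat runs moved single cells by up to about 0.7 points. The last row matches the contrast-ultrasound accuracy cited in the Introduction (92.9% and 94.4%): Φ[(1.468 + 1.589)/√2] = 0.985.

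The average hides an imbalance. At AUROC 0.76 with 18 cases, apparent sensitivity/specificity is 76%/72% against about 67%/69% in new patients: 9 points on sensitivity and 3 on specificity.

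**What makes it larger?**
- Fewer verified patients. With 40 having histology (assumed; 10 to 30 cases), the sum is overstated by 14-17 points at 0.76.
- Marker selection. Taking the best of 16 independent markers, one informative, gives 11-16 points on the sum at 0.76 but 7-9 at 0.92, no more than for the pre-chosen marker. If all 16 are equally informative at 0.8, it gives 24-29 points (18 or 36 cases). Correlated markers would give less.

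**Precision.** Exact (Clopper-Pearson) 95% intervals: 22/27 = 81%, interval 62-94%; 38/48 = 79%, interval 65-90%.

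**Does bootstrap correction work?** Partly. For the pre-chosen marker at 0.76 with 36 cases, sensitivity + specificity averaged 1.467 apparent, 1.399 corrected and 1.360 in new patients. The share removed is (1.467 − 1.399)/(1.467 − 1.360) = 0.068/0.107 = 64%.

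**The case against.** The strongest reply is that nothing in the plan says a cut-off will be chosen on the study patients. The accuracy measures are merely to be computed, and the procedures hint at a reader's overall call. If that call is the index test, no cut-off is searched for and this optimism does not arise. This stands in part: the documented fault is missing specification, and the overstatement is inferred from it. But that call is undefined and is not named as the test, and ROC analysis is the only stated route to the figures.

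The sizes also need care. The table shows sums of two measures, whereas the endpoint reports each separately. Markers as strong as the cited literature suggests would bring the bias down to about 3 points per measure. In the pre-chosen-marker runs with 75 patients, uncorrected exact intervals still covered the new-patient value 93-97% of the time, so the harm lies mainly in the point estimates. Several items, such as strictures or free fluid, read as present/absent, so cut-off searching barely applies. The contrast parameters come from one curve and are unlikely to be independent.

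Pilot status is a fair reason for having no sample size calculation and for exploring cut-offs. It does not explain an undefined primary test or missing intervals, which matter more when numbers are small.

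Three stronger readings are not supported:
- That the AUROC will be inflated. Choosing a cut-off does not inflate the AUROC of one pre-chosen marker.
- That a fitted multivariable score will be overfitted in the ROC step. The plan assigns the logistic models to association only.
- That selective histology is part of this fault. Colonoscopy is tied to high suspicion ("colonoscopy will be required to evaluate internal macroscopy features of the bowel and to obtain histological samples for conclusive diagnosis"), which is a separate issue.

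**Conclusion.** The point holds as a gap in the primary analysis with a likely, but not stated, consequence. That the plan lacks an index scan, index variable, positivity rule, intervals and internal validation is clear from the text. That the primary figures would be too favourable is conditional on the cut-off being read from the same patients, which is where ROC analysis without a preset threshold or second sample leads.

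In that case, a reasonable expectation for one pre-chosen marker is 3 to 6 points per measure on average, more on whichever of cases or non-cases is fewer. This rests on 75 verified patients, an assumed case share, normal markers and a Youden cut-off. It could be larger with fewer verified patients or with marker selection. The documents do not fix the case share, the marker strength or the method, so no single figure should be quoted as the bias of this study. The change should be made, but the gap does not make the study unworkable.

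**What to change.** Amend Statistical Analysis before outcome data are read.

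1. Name the symptom-onset scan as the primary index test and fix one positivity rule without using outcome data. The investigators should choose a rule that reflects the multiparametric study, including contrast and SWE parameters where limits can be set in advance. Record the yes/no result blind to histology. Study design calls the study ambispective, although Study duration and Data Collection describe prospective collection. For any patients included retrospectively, have the stored examination scored without access to histology, or report them separately.
2. Report the 2x2 counts, and sensitivity, specificity, PPV and NPV with exact 95% intervals. State how many scan-positive and scan-negative patients have histology.
3. Label any data-derived marker, cut-off or combined score exploratory. Give bootstrap optimism-corrected sensitivity and specificity, and a corrected AUROC where a marker or score was selected or fitted. Repeat every selection step in each resample, and state that the correction is partial.

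The cost is one data field, a paragraph of text and a little more R code, plus blinded re-scoring if there are retrospective patients. Who has colonoscopy does not change. The downsides are slightly less favourable figures and a fixed rule that may not be the best-performing one.

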## INTRODUCTION

Allogeneic stem cell transplantation (HSCT) represents a fundamental therapeutic option for patients affected by malignant hematological diseases. One of the major life-threatening complication after HSCT is acute graft versus host disease (aGvHD), especially when gastrointestinal tract is extensively involved. All grade aGvHD occurred in 40-80% of HSCT recipients, depending on donor choice, stem cell source, conditioning regimen and GvHD prophylaxis. Among patients with aGvHD, intestinal involvement accounts for 60% of the cases (1). Approximately one third of patients with intestinal aGvHD reached a grade III-IV stage with an increased risk of mortality and morbidities. The most common symptom of GI involvement of acute GVHD is diarrhea, secretory and usually voluminous, often reaching more than 1.5 liters per day. In severe cases, patients presented abdominal pain and gastrointestinal bleeding may occur, reflecting the mucosal ulceration (2). These symptoms are nonspecific given the fact they might be frequently observed after allo-SCT in *Clostridium difficile* colitis, bacterial colonization, cytomegalovirus or adenovirus infection, drug toxicity, or neutropenic enterocolitis (3). Weber et al (4) reported the use of contrast enhancement ultrasound imaging (CEUS) in diagnosing gastrointestinal aGvHD. The penetration of intravenous injected contrast microbubbles into the gut lumen showed a sensitivity of 92.9% and specificity of 94.4% for intestinal aGvHD diagnosis, but the specificity was only of 39.6% for advanced stage. On the other hand, sonographic criteria

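### The aGvHD association models have up to 16 candidate ultrasound measurements, at most 37 patients in the smaller outcome class, and no limit on model size or provision for separation

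*Combined protocol and SAP*

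**What the plan says.** The first secondary endpoint is the association between the weekly ultrasound measurements and aGvHD diagnosis in allogeneic patients. The Statistical Analysis section gives the method in one sentence: "in patients underwent to allogenic transplant uni- and multivariable logistic regression models will be used". Nothing is said about the estimator, which measurements enter, how they are selected, or what happens if a fit does not converge.

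The candidates come from Variables and Procedures. The list introduced by "The following ultrasound parameters will be collected" has seven items. The contrast-enhanced list has eight time-intensity parameters, ending with "area under the gamma curve (Area), arrive time (ATM), peak intensity (PI), change of peak intensity (I"). Shear wave elastography is added to every examination.

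Under Sample Size calculation the protocol states that "no formal sample size calculation is needed", gives a pilot rule under which "the minimum sample size required would be of 20 subjects", and then says "we plan to enroll 75 patients" on the basis of annual transplant volume. It gives no expected number of aGvHD cases.

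The interaction analysis of allogeneic against autologous patients is separate. It takes one measurement per model, so the point below does not apply to it.

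**The concern.** An unqualified reference to logistic regression is fairly read as maximum likelihood. With few outcomes per coefficient, that estimator tends to push odds ratios away from 1. When some combination of covariates separates cases from non-cases, it gives no finite estimate at all. The candidates also overlap, since several contrast parameters summarise the same curve. The change of peak intensity is not defined. If it means peak intensity minus basic intensity, then B, PI and I are exactly collinear.

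At stake is what a pilot should deliver: which measurements to carry forward, and a credible idea of how strongly each relates to aGvHD. Inflated odds ratios would exaggerate the strength of the measurements that matter. The ROC-based primary analysis is not affected.

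**Working it through.** **Candidates.** 7 (conventional ultrasound) + 8 (B, K, C, TTP, Area, ATM, PI, I) + at least 1 (shear wave) = 16.

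**Outcomes per candidate.** The figure of 75 rests on feasibility and cannot be reproduced by a calculation.

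- *Ceiling at any prevalence:* the smaller class of 75 is at most 37, and 37/16 = 2.3.
- *From the Introduction:* aGvHD occurs in 40–80% of recipients, and "Among patients with aGvHD, intestinal involvement accounts for 60% of the cases". So 0.40 × 0.60 = 24% to 0.80 × 0.60 = 48%, which is 18 to 36 of 75, or 18/16 = 1.1 to 36/16 = 2.25 per candidate. These rates describe all recipients, while the study enrols patients with diarrhoea, so the true share may be higher. The ceiling of 2.3 still holds.
- *Histology:* colonoscopy is described for high-suspicion cases. If histology defines the regression outcome, fewer than 75 patients are usable.

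**Simulation A.** Assumed: n = 75, 16 covariates, one true odds ratio of 2 per SD, 15 nulls, pairwise correlation 0.4, 24% or 48% prevalence. The median maximum-likelihood odds ratio was about 2.6 to 2.7, although one set of runs at 48% gave 2.4. Firth gave about 1.9 to 2.0. Maximum likelihood rejected a true null in 7.3–7.8% of runs.

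**Simulation B.** Assumed: n = 75, 16 covariates, four true effects, six binary measurements, latent correlation 0.3, Wald intervals, 600 runs per setting. The maximum-likelihood medians use non-separated runs only.

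| True OR | Prevalence | Separated | Median OR, ML | Median OR, Firth |
|---|---|---|---|---|
| 2 | 24% | 18.8% | 3.31 | 1.96 |
| 2 | 36% | 4.8% | 2.96 | 1.99 |
| 2 | 48% | 2.8% | 2.75 | 1.92 |
| 3 | 24% | 58.7% | 8.37 | 2.74 |
| 3 | 36% | 31.0% | 6.12 | 2.72 |
| 3 | 48% | 25.5% | 6.16 | 2.84 |

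With only 40 verified patients (true odds ratio 2, 48% prevalence), 77% of fits were separated.

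**Smaller models, n = 75, true odds ratio 2, 24% or 48% prevalence.** The maximum-likelihood median was 2.04–2.06 with one covariate, 2.11 with two and 2.18–2.25 with four, with no separation. At a true odds ratio of 3, models with 3 to 8 covariates gave 3.3–4.5 by maximum likelihood and 2.7–3.0 by Firth.

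**Cost of the penalty.** With 16 covariates and a true odds ratio of 2, Firth detected the effect in 22–31% of runs, against 29–42% for maximum likelihood in its non-separated runs. Part of the latter reflects a null rejection rate of up to about 8%. With four covariates the figures were 38% against 44% at 24% prevalence, and 52% against 58% at 48%. In the 16-covariate Firth fits the median standard error of the log odds ratio was 0.44–0.51. The 95% limits therefore lie a factor of exp(1.96 × 0.44) = 2.4 to exp(1.96 × 0.51) = 2.7 either side of the estimate.

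**The case against.** The strongest reply is that the plan never says all 16 measurements enter one model. Sixteen is an upper bound. Where the SAP does specify a model, in the interaction analysis, it uses one measurement at a time. Small maximum-likelihood models are nearly unbiased at moderate effects, and this is a secondary endpoint in a declared pilot. All of that stands. It limits the claim to what happens if many measurements are fitted together, but nothing in the plan prevents that.

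Three stronger readings are tempting and are not supported:

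- *That the odds ratios are bound to be inflated or infinite.* This depends on model size, event count and effect strength, none of which the plan fixes.
- *That univariable models are equally at risk, because the Introduction quotes 92.9% sensitivity and 94.4% specificity.* Those figures describe microbubble penetration into the gut lumen, which is not on either measurement list. They describe no planned predictor.
- *That a penalised fit settles the matter free of charge.* It shrinks estimates, lowers the rejection rate and adds no information. It does not cure exact collinearity either: the information matrix is then singular and the Firth penalty is undefined, so a variable has to be dropped.

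It is also fair to object that weekly measurements would give several rows per patient. That clustering is a separate matter, which neither the simulations nor the penalty addresses.

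**Conclusion.** The concern holds in conditional form. The plan allows up to 16 candidates against at most 37 patients in the smaller outcome class, and sets no limit on model size and no rule for separation. If many measurements are fitted together by maximum likelihood, a true odds ratio of 2 would typically be reported as about 2.6 to 2.7 with one real effect, and about 2.75 to 3.3 with four. Non-finite estimates become common with stronger effects or fewer verified patients. With one to three covariates and moderate effects the distortion is slight.

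The counts come from the protocol. The inflation figures rest on assumed effects, correlations and prevalences that it does not give, and on reading the unnamed estimator as maximum likelihood.

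**What to change.** In the Statistical Analysis section, for the aGvHD association models:

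1. Limit the multivariable model to a short, named list of measurements fixed before data lock. The choice is the investigators'.
2. Define the change of peak intensity, and do not enter parameters that are functions of one another. B, PI and I should not appear together if I is PI minus B.
3. Fit the multivariable model by Firth-penalised logistic regression with profile-likelihood intervals. Use the same fit for any univariable model that shows separation.
4. Label the results exploratory.

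This changes SAP wording only, and the analysis can stay in R, which is already specified. The downside is somewhat smaller odds ratios, fewer nominally significant results and fewer measurements in the multivariable table. The intervals will still be wide.
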